9.6. Data management

All responsible parties shall adhere to good documentation practice (GDocP) for all maintained records and any applicable changes to these.

9.6.1 Data Collection Methods

- The Investigator will maintain complete and accurate paper format study documentation in a separate file. Study documentation may include medical records, records detailing the progress of the study for each patient, signed informed consent forms, correspondence with the Ethics Committee (EC) and the Monitor, and data clarifications requested by Data Management (DM)/responsible party.
- Case report forms (CRFs) will be provided in electronic form (i.e. eCRF).
- The Investigator will comply with the procedures for data recording and reporting.
- The handling of data by the responsible party, including data quality assurance, will comply with regulatory guidelines and the standard operating procedures of the responsible party. DM and control processes specific to the study will be described in the DM plan.

9.6.2 Electronic Case Report Forms (eCRFs)

- The eCRF will be provided by the Sponsor and will be used to collect all data. Data will be obtained from the patient 's medical record.
- All information entered in the eCRF is considered to accurately display original data. The
 Investigator is responsible for patient data procuration and for the quality of data
 recorded in the patient 's eCRF. Access to the eCRF is restricted by username and
 password.
- For each patient in the study, an eCRF will be completed and signed electronically by the Investigator. The eCRFs may also be completed by trained and authorized personnel at the investigational site. The completed eCRFs are the sole property of the Sponsor and should not be made available in any form to 3rd parties without written permission of the Sponsor, except for authorized representatives of appropriate governmental health or regulatory authorities, without written permission of the Sponsor.

- During data entry and after completion of the entry process, computer logic checks will be run to identify items, such as inconsistent dates, missing data, and questionable values. Queries may be issued by Sponsor personnel (or designees) and will be answered by authorized personnel at the site.
- Errors occurring in eCRFs will be modified by the Investigator and all changes will be tracked in the audit trail that captures respective changes.
- In no case the eCRF is to be considered as source data for this study.

9.6.3 Database management

- After the data have been entered and verified, various edit checks will be performed for the purpose of ensuring the accuracy, integrity, and validity of the database. After last patient out, when the database is complete and accurate, it will be locked. Any changes to the database after that time can only be made by joint written agreement between the Sponsor, the study statistician and the data manager. An interim database lock is planned after completion of Part A.
- It is the responsibility of the Investigator to resolve all data queries forwarded by DM in a timely manner.
- Adverse events, prior and concomitant illnesses/medications will be coded using the Medical Dictionary for Regulatory Activities (MedDRA). Drugs will be coded using the World Health Organization (WHO) Anatomical Therapeutic Chemical (ATC) classification system. Coding will start after completion of Part A, by using the last version of the dictionaries available at that timepoint.

9.6.4 Handling of protocol deviations

- Except for a situation in which proper care for protection, safety and well-being of the study patients requires medical treatment, the study will be conducted as described in the approved protocol.
- Any deviation from the study protocol (i.e. any deviation from the routine clinical practice that follows the recommendations in the product information of ropeginterferon alfa-2b) in the conduct or documentation of the study will be notified to the Sponsor (by the Investigator and/or Monitor) on ongoing basis and explained by the Investigator. Protocol deviations will be documented in the monitoring visit report and/or in a cumulative listing.
- All protocol deviations will be recorded in the eCRF.

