The recommended posology for the titration phase of ropeginterferon alfa-2b results in a prolonged time to reach the individual optimal dose compared to hydroxycarbamide. In a phase III clinical study in PV (PROUD-PV; EudraCT number 2012-005259-18), the end of the mean individual titration phase for ropeginterferon alfa-2b was reached after approximately 3.7 months, for hydroxycarbamide after approximately 2.6 months of treatment. Thus, other products (e.g. hydroxycarbamide) may be preferred in patients for whom an early reduction in elevated blood counts is necessary to prevent thrombosis and bleeding. During the titration phase the effectiveness to reduce the cardiovascular and thromboembolic risk of the underlying disease may not be fully established.

Risk minimization measures for the important, identified risk of "hepatotoxicity"

The routine risk communication in the Summary of Product Characteristics (SmPC) and Patient Information Leaflet (PIL) and legal status (prescription only medicine) implemented in the EMA approved Risk Management Plan for ropeginterferon alfa-2b (Version 1.0, dated 13DEC2018) are considered sufficient to manage the important identified risk "hepatotoxicity".

Evaluation of the effectiveness of risk minimization measures for the important, identified risk "hepatotoxicity" during this post-authorization safety study will focus on the risk communication in the SmPC. Specifically, on the recommendations on hepatic enzyme monitoring during long-term treatment with ropeginterferon alfa-2b and dose adjustments (including dose changes or treatment discontinuation) in case of adverse events.

8. Research question and objectives

In addition to the routine pharmacovigilance activities, AOP Orphan Pharmaceuticals AG proposed to the EMA to conduct this post-authorization safety study to address the effectiveness of the risk minimization measures for the important, identified risk of hepatotoxicity and to evaluate the cardiovascular safety within the cohort of patients with PV and treated with ropeginterferon alfa-2b.

The main research question is: "What is the incidence rate of the important, identified risk "hepatotoxicity" in PV patients newly treated with ropeginterferon alfa-2b in routine post-authorization use?"

1. Primary objective

• To assess the incidence rate of the important, identified risk "hepatotoxicity" in PV patients newly treated with ropeginterferon alfa-2b in routine post-authorization use.

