9.1. Study design

This is a prospective, multicentre, non-interventional, observational, post-authorization safety study of ropeginterferon alfa-2b in adult PV patients.

The purpose of the study is to conduct analyses of safety data related to ropeginterferon alfa-2b treatment. The study will be conducted in two parts over 18 months for the assessment of safety:

- Part A: observation of patients during the first 6 months of ropeginterferon alfa-2b treatment for the evaluation of hepatotoxicity and major cardiovascular adverse events (interim analysis after 6 months)
- Part B: observation for an additional 12 months of ropeginterferon alfa-2b treatment for the evaluation of hepatotoxicity and major cardiovascular adverse events

Participation will be offered to patients who receive ropeginterferon alfa-2b in the frame of clinical routine. Due to the non-interventional nature of this study, the decision to prescribe ropeginterferon alfa-2b is clearly separated from inclusion.

Ropeginterferon alfa-2b therapy will be in accordance with the physician´s routine clinical practice (who is experienced in the management of PV) and with the recommendations in the product information for ropeginterferon alfa-2b (Annex 1).

Safety endpoints:

- Liver enzymes (i.e. ALT, AST, GGT), and bilirubin
- Cardiovascular events (thromboembolic adverse events and major adverse cardiac events [MACE])
- Treatment-emergent hepatobiliary adverse drug reactions
- All treatment-emergent adverse events

Evaluation of effectiveness of risk minimization measurements for the important, identified risk "hepatotoxicity":

The effectiveness of the recommendation to monitor hepatic enzymes during long-term ropeginterferon alfa-2b treatment as described in section 4.4 of the SmPC will be evaluated by assessing the frequency of hepatic enzyme and bilirubin evaluation in routine clinical practice.

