9.2.8 Patient 's dose change/ dose interruption

The recommendations in the product information for ropeginterferon alfa-2b dosing (including dose changes or temporarily treatment interruption) should be followed (Annex 1). Any ropeginterferon alfa-2b dose change/interruption has to be documented including the reason for

dose change/interruption. A temporary ropeginterferon alfa-2b treatment interruption is no reason for study discontinuation.

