9.7. Data analysis

9.7.1 Datasets and analysis cohorts

Safety dataset:

The safety dataset will contain all patients who were enrolled in this study, received ropeginterferon alfa-2b treatment at least once during routine medical setting and from whom data is available.

• Full analysis dataset:

The full analysis dataset 1 (FAS1) will contain all patients who completed Part A of the study. The full analysis dataset 2 (FAS2) will contain all patients who completed Part B of the study.

• Per protocol dataset:

The per protocol set (PPS) will consist of patients included in the FAS who complete a certain pre-specified minimal exposure to the treatment regimen, have all measurements needed for assessment of the primary endpoint available and do not violate the study protocol in major concerns.

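### Section 9.6.4 treats departures from the product information as reportable protocol deviations, although a secondary objective measures liver monitoring and dose adjustment in routine practice as outcomes

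*Protocol*

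**What the plan says.** **What is to be measured.** Section 8 says the study was proposed "to address the effectiveness of the risk minimization measures for the important, identified risk of hepatotoxicity" and to evaluate cardiovascular safety. Formally, risk minimisation is a secondary objective; the primary objective is the incidence rate of hepatotoxicity. Section 7 narrows the evaluation to the risk communication in the SmPC: "Specifically, on the recommendations on hepatic enzyme monitoring during long-term treatment with ropeginterferon alfa-2b and dose adjustments". Section 9.1 states that the monitoring recommendation "will be evaluated by assessing the frequency of hepatic enzyme and bilirubin evaluation in routine clinical practice", and that the dose-adjustment advice is assessed through the rate of adjustments or discontinuations due to hepatotoxicity. Sections 9.3.2 and 9.7.2.4 list the corresponding variables and endpoints.

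**How departures are handled.** Section 9.6.4 explains a deviation, after an i.e., as "any deviation from the routine clinical practice that follows the recommendations in the product information of ropeginterferon alfa-2b". The same sentence confines deviations to the running and documentation of the study. Each deviation "will be notified to the Sponsor (by the Investigator and/or Monitor) on ongoing basis and explained by the Investigator". The section ends: "All protocol deviations will be recorded in the eCRF".

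**Related text.** Section 9.2.8 says that product-information dosing advice should be followed and asks for the reason for any dose change or interruption. Section 9.2.6 prescribes no visit schedule because the study is non-interventional. Section 9.7.1 limits the per protocol set to patients who, among other conditions, "do not violate the study protocol in major concerns".

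**The concern.** Whether physicians act on the SmPC without further prompting is what the risk-minimisation evaluation sets out to learn. A duty to report and explain each departure is a form of oversight that does not exist in ordinary use. If it changes behaviour, the study describes the SmPC plus study oversight, and the routine measures may look more effective than they are.

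The effect need not stop at the secondary objective. The primary endpoint in Section 9.7.2.1 includes significant elevations of liver enzymes or bilirubin. Section 9.3.1.1 leaves diagnostic procedures to patient need and enters results as available. An elevation is found only if a test is done, so a change in testing frequency can change the detected incidence.

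**Working it through.** No sample size, rate or error probability enters this point, so there is no plan figure to reproduce. The check sets the sections side by side.

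1. **Is the behaviour an outcome?** Yes. Section 9.7.2.4 lists eight endpoints. The first two are the behaviours themselves: frequency of liver-parameter evaluation, and frequency of dose adjustment or discontinuation in case of hepatotoxicity. Five more concern what happens after a dose reduction or discontinuation, so the patients who enter them depend on the same behaviour. The eighth counts hepatobiliary events after significant elevations, which must first be detected by testing.

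2. **Does the deviation rule cover that behaviour?** On its wording, yes. The i.e. clause describes clinical departures from practice that follows the product information, and names no other kind of deviation. Sections 7 and 9.1 say that the SmPC contains the recommendations on hepatic enzyme monitoring and on dose adjustment or discontinuation. A physician who departs from them therefore falls within the definition.

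3. **Does the qualifier take it out again?** Not clearly. Confining deviations to how the study is run or documented points towards study procedures, but the clause meant to explain the term points to clinical practice. The two halves pull apart, and the explanatory clause is the more specific.

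4. **Is there an exemption elsewhere?** None was found in Sections 9.1, 9.2.6, 9.2.8, 9.3.2, 9.7.1, 9.7.2.4 or 9.8.3. Section 9.8.3 adds regular monitor visits that check adherence to the protocol.

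5. **Which direction would an effect take?** Having to notify and explain departures gives a reason to avoid them. Any reactivity would therefore tend to raise observed testing and adjustment frequencies.

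6. **How large?** Not derivable. The documents give no expected adherence, no target and no measure of how sites respond to deviation reporting. The product information in Annex 1 is a stand-alone document that is not at hand, so how specific its monitoring advice is, and how often a departure could be identified, cannot be judged. An assumed share of non-adherent patients multiplied by the planned 228 would count hypothetical deviations; it would not measure bias in any endpoint.

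**The case against.** The strongest reply is that Section 9.6.4 asks only for notification, explanation and recording. It provides for no correction, retraining, sanction or withdrawal. No section mandates a liver test, and no visit schedule is imposed. Any prospective study with site monitoring carries some reactivity. All of this stands. A reader might infer that the protocol enforces adherence, or that the results are bound to be inflated; the text supports neither. It supports a possible effect with a likely direction.

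A reader might also infer that the per protocol set will remove non-adherent patients from the risk-minimisation analysis. The protocol does not say so. No section assigns the Section 9.7.2.4 endpoints to that set, what counts as a major violation is not defined, and both matters are commonly left to the SAP. The safety dataset keeps every enrolled and treated patient with data, whatever the adherence.

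Nor does Section 9.2.8 by itself contradict the non-interventional design. It concerns dosing, not liver monitoring; on-label use is already an inclusion criterion; and the reasons for dose changes are needed for the endpoints on reductions or discontinuations due to elevations.

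These replies leave the definition in Section 9.6.4 untouched. An SAP could settle the analysis sets, but it could not undo prompting that sites had received during conduct. Recording departures is not the problem; classing them as deviations that require an explanation is.

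**Conclusion.** The point holds as an avoidable conflict of wording with a plausible effect on a secondary objective. Section 9.6.4, read by its own explanatory clause, makes a reportable deviation of behaviour that Sections 9.1, 9.3.2 and 9.7.2.4 treat as outcome, and nothing exempts it. Followed as written, it may move observed liver testing and dose adjustment towards the SmPC, and may also affect the number of elevations detected.

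The size is unknown. The direction rests on the assumption that sites respond to a reporting duty by departing less often. It would be too strong to say that measuring adherence is the aim of the whole study: the primary objective is hepatotoxicity incidence, and the listed measures are frequencies, rates and later outcomes, not a percentage adherent to the SmPC. The case for acting is that the remedy is cheap, not that a large bias has been shown.

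**What to change.** - **Section 9.6.4:** limit protocol deviations to study procedures, namely consent, eligibility, safety reporting and data recording. State that departures from product-information advice on liver monitoring or dose adjustment are recorded as outcome data for Section 9.7.2.4 and are not handled as deviations needing explanation.
- **Section 9.7.1 or 9.7.2.4:** state that the Section 9.7.2.4 endpoints are analysed in the safety dataset, so that such departures do not remove patients from them.
- **Section 9.2.8:** reconcile its wording with the above. Keep the documentation of dose changes and their reasons, which the endpoints need. No clinical rule is to be changed.
- **Monitoring plan:** align what monitors check as protocol adherence.

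The cost is a few sentences and slightly less prompting of sites. Safety-reporting duties, data collection and sample size are unaffected.

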9.7. Data analysis

9.7.1 Datasets and analysis cohorts

Safety dataset:

The safety dataset will contain all patients who were enrolled in this study, received ropeginterferon alfa-2b treatment at least once during routine medical setting and from whom data is available.

• Full analysis dataset:

The full analysis dataset 1 (FAS1) will contain all patients who completed Part A of the study. The full analysis dataset 2 (FAS2) will contain all patients who completed Part B of the study.

• Per protocol dataset:

The per protocol set (PPS) will consist of patients included in the FAS who complete a certain pre-specified minimal exposure to the treatment regimen, have all measurements needed for assessment of the primary endpoint available and do not violate the study protocol in major concerns.

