9.2.7 Patient withdrawal and patient discontinuation

Any patient may voluntarily withdraw consent for continued participation and data collection. The reason for withdrawal will be recorded on the eCRF page. The data collected on withdrawn patients will be used in the analyses and included in the study report.

Study discontinuation (i.e. complete withdrawal from study participation) may be due to:

- Dropout of the patient (i.e. active discontinuation by patient).
- Patient is lost to follow-up (i.e. discontinuation by patient without notice or action; the Investigator should contact the patient either by telephone or through a clinic visit to establish as completely as possible the reason for the withdrawal.).
- Discontinuation of the patient on Investigator´s discretion if, in his/her judgement, continued participation would pose an unacceptable risk for the patient.

In case the patient discontinues the study (i.e. discontinuation of ropeginterferon alfa-2b treatment), the Investigator should collect and document information on new PV therapy. In case of ropeginterferon alfa-2b treatment discontinuation due to hepatotoxicity, follow-up of the AE as performed in routine clinical practice (e.g. evaluation of hepatic enzymes) should be documented.

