9.2.9 Patient completion

A patient is considered to have completed the study when he/she ceases active participation in the study because the patient has, or is presumed to have, completed all study procedures according to the protocol (see Figure 1).

Completion will be documented on the respective eCRF page, including the reason for completion (e.g. study completed, screening failure, adverse event occurrence [e.g. death], study discontinuation (section 9.2.7)). Regardless of the reason, all data available for the patient up to the time of completion should be recorded on the appropriate eCRF pages.

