9.7.2 Methods of analysis

9.7.2.1 Primary safety endpoint

Incidence of (1) significant elevations of liver enzymes ALT, and/or AST, and/or GGT (≥3 times ULN) and/or bilirubin (>2 times ULN), and (2) treatment-emergent hepatobiliary adverse drug reactions in Part A (i.e. first 6 months of treatment).

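### FAS1, FAS2 and the PPS are completer sets that select on a consequence of the outcome, and Section 9.7.2 does not tie the incidence endpoints to the safety dataset that avoids this

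*Protocol*

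**What the plan says.** Protocol Section 9.7.1 defines the datasets:

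- **All treated patients:** "The safety dataset will contain all patients who were enrolled in this study, received ropeginterferon alfa-2b treatment at least once during routine medical setting", provided data are available. Completion is not required. It is the only dataset named in the abstract's data analysis paragraph.
- **FAS1:** "The full analysis dataset 1 (FAS1) will contain all patients who completed Part A of the study".
- **FAS2:** "The full analysis dataset 2 (FAS2) will contain all patients who completed Part B of the study".
- **PPS:** "patients included in the FAS who complete a certain pre-specified minimal exposure to the treatment regimen". These patients must also have all primary-endpoint measurements and no major protocol violation.

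Three other places bear on who is in these sets:

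- **Section 9.2.7** glosses study discontinuation as discontinuation of ropeginterferon alfa-2b. It also promises: "The data collected on withdrawn patients will be used in the analyses and included in the study report".
- **Section 9.2.9** gives as possible reasons for completion: "study completed, screening failure, adverse event occurrence [e.g. death], study discontinuation".
- **Section 9.7.2.1** sets the primary endpoint as the incidence of significant liver-parameter elevations and "treatment-emergent hepatobiliary adverse drug reactions in Part A (i.e. first 6 months of treatment"). Neither it nor Section 9.7.2.2 names a dataset.

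Section 9.5 sizes the study for 178 'evaluable' patients followed for all 18 months, although the primary endpoint ends at 6 months. Section 9.9 argues that the dropout allowance protects evaluation of the primary endpoint.

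**The concern.** A full analysis set normally keeps everyone who entered and was treated. Here the sets with that name keep only those who reached the end of the part. Stopping treatment is a possible consequence of the outcome being counted: Section 9.7.2.4 makes discontinuation for hepatotoxicity an endpoint in its own right. A set that excludes people who stopped therefore selects on something that the outcome can cause.

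Two consequences need no assumed figure. MACE includes cardiovascular death (Section 9.3.1.1), and a patient who dies in Part A does not, on the plain reading, complete it, so FAS1 would hold no Part A cardiovascular deaths. Likewise, FAS1 could not show the patients who stopped for hepatotoxicity during Part A.

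At stake is the primary objective of a safety study committed to the EMA. If cases leave more often than other patients, a completer analysis errs toward understating risk.

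**Working it through.** **1. Membership, reading the sections together.** Stopping the drug is leaving the study (9.2.7). Leaving before month 6 is not completing Part A. FAS1 holds Part A completers, and the PPS lies inside the FAS (9.7.1). So a patient who stops in month 3 for a liver elevation is in the safety dataset but not in FAS1 or the PPS. The only other reading comes from 9.2.9, where death and discontinuation are reasons for completion. On that reading 'completed Part A' no longer separates anyone. The definition is either selective or indeterminate.

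**2. The plan's own figures.**
- One-year incidence of 23.6% (9.5), constant hazard: 1 − (1 − 0.236)^0.5 = 12.6% at 6 months, as stated.
- One-year dropout of 20%: 1 − 0.8^1.5 = 28.4% at 18 months; 28.5% is stated.
- Wald interval for 21/169: 7.5% to 17.4%, as stated.

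**3. Part A incidence in a completer set, total dropout fixed at the plan's 10%** (9.9). Take 228 patients, so 228 × 0.126 = 28.7 cases, 22.8 dropouts and 205.2 completers. Let f be the share of cases who leave before month 6. The documents give no value for f; the range is assumed.

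Reading in FAS1 = 28.7 × (1 − f) / 205.2

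| f | cases lost | share of all dropouts | FAS1 reads |
|---|---|---|---|
| 0% | 0 | 0% | 14.0% |
| 10% | 2.9 | 13% | 12.6% |
| 25% | 7.2 | 32% | 10.5% |
| 50% | 14.4 | 63% | 7.0% |
| 75% | 21.5 | 94% | 3.5% |

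The reading falls below 12.6% only when f exceeds the overall 10%, that is, when cases leave more often than non-cases.

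**4. Same question, with f as loss of cases on top of unrelated dropout.** Reading = p(1 − f)/(1 − fp).
- f = 25%: 0.126 × 0.75 / (1 − 0.0315) = 9.8%.
- f = 50%: 0.126 × 0.50 / (1 − 0.063) = 6.7%.

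The two set-ups agree on about 10% and about 7%. At f = 50% both fall below the plan's 7.5% to 17.4%.

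**5. Eighteen months.** Carrying the constant hazard forward (an extrapolation) gives p = 1 − 0.764^1.5 = 33.2%, or 75.7 cases. With dropout fixed at 28.5% there are 163.0 completers. FAS2 then reads 34.8% at f = 25%, 33.2% at f = 28.5% and 23.2% at f = 50%. With f as excess loss, the readings are 27.2% at 25% and 19.9% at 50%. The direction again depends on whether cases leave in excess.

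**6. Why the safety dataset also needs follow-up time.** It removes no case, but patients who leave early contribute less observation. With independent constant hazards for event and exit, the expected share seen to have an event in Part A is [ln 0.874 / (ln 0.874 + ln 0.9)] × (1 − 0.874 × 0.9) = 0.561 × 0.213 = 12.0%, against 12.6%. The shortfall is small but avoidable.

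**The case against.** The strongest reply is that the protocol already has the right set. The hepatotoxicity and cardiovascular incidences are headed as safety endpoints, a safety dataset without a completion condition stands in the same section, and the abstract names no other. Endpoints such as normalisation after discontinuation need a set that keeps discontinuers, and liver follow-up after stopping is documented (9.2.7, 11.2). Linking endpoints to datasets is commonly left to the SAP, which is not shown here.

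Much of this stands, and it rules out two stronger readings. A reader might infer that patients who stop for hepatotoxicity *are* removed from the hepatotoxicity incidence. The documents do not support that: no section assigns an incidence to FAS1, FAS2 or the PPS. A reader might also infer that 9.7.1 contradicts the promise in 9.2.7 to use withdrawn patients' data. It does not, because the safety dataset honours that promise.

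Nor is downward bias certain. Section 7 describes the elevations as mostly transient, and Section 9.2.8 says a temporary interruption is no reason to leave, so many cases may stay. A case loss of 50% in Part A would make cases about 63% of all expected dropouts, and nothing in the documents supports so high a figure.

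What the reply does not answer is what the protocol itself fixes. It gives the name 'full analysis' to completers and lets 'completed' carry two meanings. It also sizes the primary endpoint on patients remaining after dropout, and the only dataset definition that mentions the primary endpoint is the PPS. An SAP author following that text could reasonably choose a completer set.

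**Conclusion.** The point holds conditionally. FAS1, FAS2 and the PPS, read plainly with Section 9.2.7, condition on a consequence of the outcome and are unsuitable for the incidence endpoints. The safety dataset is suitable, but Section 9.7.2 does not name it, and Sections 9.5 and 9.9 lean the other way.

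If a completer set were used, a true Part A incidence of 12.6% would read about 10% with 25% of cases leaving early and about 7% with 50%. This rests on the plan's incidence and dropout figures and on assumed shares of cases lost. With no excess loss there is no downward bias, and if cases left less often than others the reading would be too high (up to 14.0%). The loss of Part A cardiovascular deaths from FAS1 depends on no such share, only on the plain reading of 'completed'.

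**What to change.** - **Sections 9.7.1 and 9.7.2:** state that the primary endpoint and all hepatotoxicity and cardiovascular incidence endpoints are analysed in the safety dataset. Count every event before exit and account for follow-up time, either by person-time rates or by cumulative incidence with censoring at exit and death as a competing event.
- **Section 9.7.1:** rename FAS1 and FAS2 as completer sets, and use them and the PPS for supportive analyses only.
- **Sections 9.2.7, 9.2.9 and 9.7.1:** reconcile the meaning of 'completed', so that reaching the end of a part is distinguished from ending participation for another reason.
- **Section 9.5:** define 'evaluable' so that a patient with an event before exit counts. A definition requiring observation through to month 6 or month 18 would bring the completer condition back.

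The cost is protocol and SAP wording, ideally before the interim database lock after Part A. No new data are needed: events before exit are already recorded, as is liver follow-up after stopping for hepatotoxicity.
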